11.2.2 Major Secondary Endpoints

Laboratory parameters of interest (neutrophils, platelets, hepatobiliary parameters, and lipid parameters) will be observed. Toxicity grade will be summarized by treatment group over time through the end of the study.

11.2.3 Other Secondary Endpoints

In addition to the primary and major secondary efficacy endpoints, the following efficacy endpoints will be summarized by treatment group over time through the end of the study:

1. Proportion of subjects who achieve ACR 20 response
2. Proportion of subjects who achieve ACR 50 response
3. Proportion of subjects who achieve ACR 70 response
4. Proportion of subjects with DAS28 (CRP) response
5. Proportion of subjects with DAS28 (CRP) remission
6. Change from baseline in DAS28 (CRP)
7. Proportion of subjects with SDAI-based ACR/EULAR remission
8. Proportion of subjects with Boolean-based ACR/EULAR remission
9. Change from baseline in SDAI
10. Change from baseline in CDAI
11. Change from baseline in HAQ-DI
12. Proportion of HAQ-DI responders (ie, those who have a change from baseline of > 0.22 in HAQ-DI score)
13. Change from baseline in PCS and MCS and in domain scores of SF-36
14. Change from baseline in duration of morning stiffness

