9.2.1.2 Pain Assessment

Subjects will be asked to assess their average pain during the past week on a visual analogue scale (VAS). The scale ranges from “no pain” to “the worst possible pain”. This assessment should be completed prior to the joint examination. The validity of this assessment has been evaluated and reviewed extensively as it is a component of the ACR response score.^{8,15} Specific magnitudes of change in the VAS correspond to prespecified ACR score calculations (ie, a 20% improvement in the VAS corresponds to an ACR 20).

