9.2.1.4 Health Assessment Questionnaire – Disability Index

The functional status of the subject will be assessed using the HAQ-DI.¹² This 20-question instrument assesses the degree of difficulty a person has in accomplishing tasks in 8 functional areas (dressing, arising, eating, walking, hygiene, reaching, gripping, and activities of daily living). Responses in each functional area are scored from 0, indicating no difficulty, to 3, indicating inability to perform a task in that area.

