9.2.2 Definitions

9.2.2.1 American College of Rheumatology Responses

ACR responses are presented as the numerical measurement of improvement in multiple disease assessment criteria. For example, an ACR 20 response⁹ is defined as:

1. $\geq 20\%$ improvement from baseline in both swollen joint count (66 joints) and tender joint count (68 joints),

AND

2. $\geq 20\%$ improvement from baseline in 3 of the following 5 assessments:

Patient's assessment of pain (VAS)

Patient's Global Assessment of Disease Activity (VAS)

Physician's Global Assessment of Disease Activity (VAS)

Patient's assessment of physical function as measured by HAQ-DI

C-reactive protein (CRP)

ACR 50 and ACR 70 are similarly defined except improvement threshold from baseline is 50% and 70%, respectively.

9.2.2.2 Disease Activity Index Score 28

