9.2.2.2.1 Disease Activity Index Score 28 Using CRP

The Disease Activity Index Score 28 using CRP [DAS28 (CRP)] is a derived score combining tender joints (28 joints), swollen joints (28 joints), CRP, and Patient's Global Assessment of Disease Activity (GH).⁴⁵ The DAS28 (CRP) is a continuous parameter and is defined as follows:

$$\text{DAS28 (CRP)} = 0.56 \times \text{SQRT}(\text{TEN28}) + 0.28 \times \text{SQRT}(\text{SW28}) + 0.36 \times \ln(\text{CRP} + 1) + 0.014 \times \text{GH} + 0.96$$
 where:

- The set of 28 joint count is based on evaluation of the shoulder, elbow, wrist, MCP1, MCP2, MCP3, MCP4, MCP5, PIP1, PIP2, PIP3, PIP4, PIP5 joints of both the upper right extremity and the upper left extremity as well as the knee joints of lower right and lower left extremities.
- TEN28 is 28 joint count for tenderness.
- SQRT (TEN28) is square root of TEN28.

CNTO 136 (sirukumab): Clinical Protocol CNTO136ARA3004 – Amendment 3

- SW28 is 28 joint count for swelling.
- SQRT (SW28) is square root of SW28
- Ln (CRP+1) is natural logarithm of (CRP value [mg/L] + 1).
- GH is Patient’s Global Assessment of Disease Activity on VAS.

9.2.2.2.1.1 DAS28 (CRP) Response

- DAS28 (CRP) response is defined in [Table 3](#).⁴⁵

Table 3: DAS28 (CRP) response criteria			
DAS28 (CRP) at the visit	Improvement from Baseline		
	> 1.2	> 0.6 – 1.2	≤ 0.6
• ≤ 3.2	• Good response	• Moderate response	• No response
• > 3.2 – 5.1	• Moderate response	• Moderate response	• No response
• > 5.1	• Moderate response	• No response	• No response

9.2.2.2.1.2 DAS28 (CRP) Remission

DAS28 (CRP) remission is defined as a DAS28 (CRP) value of < 2.6 at a visit.

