11.2 Efficacy and Safety Analyses

Baseline value in efficacy and safety is defined as the baseline value of study CNTO136ARA3002 or CNTO136ARA3003. No missing data imputation will be used.

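### Does the HAQ-DI responder rule need a stated direction for its 0.22 threshold?

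*Protocol*

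**What the plan says.** Section 11.2.3 of the protocol lists 14 other secondary efficacy endpoints, to be summarised by treatment group over time. Item 11 is "Change from baseline in HAQ-DI". Item 12 is the "Proportion of HAQ-DI responders (ie, those who have a change from baseline of > 0.22 in HAQ-DI score". No other HAQ-DI responder definition appears in the protocol: Section 9.2.2 defines ACR response, DAS28 response and remission, SDAI, CDAI and ACR/EULAR remission, and Section 9.2.3 names the HAQ-DI only as an instrument.

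Section 9.2.1.4 fixes the direction of the scale: "Responses in each functional area are scored from 0, indicating no difficulty, to 3, indicating inability to perform a task in that area". Section 11.2 fixes the reference point: "Baseline value in efficacy and safety is defined as the baseline value of study CNTO136ARA3002 or CNTO136ARA3003". Neither section says whether change means visit minus baseline or the reverse.

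**The concern.** A responder rule should be reproducible from its own words, and this one needs a sign that is not written down. If an analyst computes change as visit minus baseline, a value above 0.22 is a worsening, so the literal rule picks the wrong subjects. If change is read as absolute, improvement and deterioration are mixed. Only a decrease gives the evident meaning.

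The omission stands out because the neighbouring response rules do state direction. ACR 20 requires "improvement from baseline in both swollen joint count (66 joints) and tender joint count (68 joints" by at least 20%; for the higher levels, "ACR 50 and ACR 70 are similarly defined except improvement threshold from baseline is 50% and 70%, respectively"; and the DAS28 (CRP) response table is headed "Improvement from Baseline". At stake would be a reported HAQ-DI responder rate that measures something other than response, possibly repeated in the integrated analyses that Section 11 places under a separate SAP.

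**Working it through.** The protocol gives no planned figure for HAQ-DI response, so there is nothing to reproduce. The check has three parts.

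**1. What each reading counts.** Inputs: the 0.22 threshold (Section 11.2.3, item 12) and higher scores being worse (Section 9.2.1.4). The two subjects are invented.

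| Subject | Baseline | Visit | Visit − baseline > 0.22 | Absolute change > 0.22 | Baseline − visit > 0.22 |
|---|---|---|---|---|---|
| A (improves) | 1.50 | 1.00 | −0.50: no | 0.50: yes | 0.50: yes |
| B (worsens) | 1.00 | 1.50 | 0.50: yes | 0.50: yes | −0.50: no |

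Only the last column counts improvement alone, so the observation about the wording is correct.

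**2. Which reading the protocol supports.**

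- The threshold clause is introduced as an explanation of the word responders, under a heading for efficacy endpoints. A responder who has lost function contradicts the term being defined. That excludes the first reading, and it excludes the second because that one would also count subject B.
- Section 9.2.1.2 speaks of magnitudes of change in the pain VAS and then explains them by example: "a 20% improvement in the VAS corresponds to an ACR 20". On a scale where higher is worse, the authors write change and mean improvement.
- The DAS28 response table gives improvement as positive amounts (> 1.2, > 0.6), although a lower DAS28 is better; remission is a value below 2.6. A positive 0.22 for HAQ-DI response follows the same style.
- The visit-minus-baseline convention, needed for the rule to select worsening, is common in practice but appears nowhere in the protocol.

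**3. How different the answers would be if someone did misread it.** The documents give no HAQ-DI distribution, so this is an assumption: change (visit − baseline) is Normal with mean *m* and SD *s*.

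- Intended share: Φ((−0.22 − *m*)/*s*)
- Reversed share: 1 − Φ((0.22 − *m*)/*s*)
- Absolute share: the sum of the two

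For *m* = −0.4 and *s* = 0.6:

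- Intended: Φ(0.18/0.6) = Φ(0.30) = 61.8%
- Reversed: 1 − Φ(0.62/0.6) = 1 − Φ(1.033) = 15.1%
- Absolute: 61.8% + 15.1% = 76.9%

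Over *m* from −0.2 to −0.6 and *s* from 0.5 to 0.7, the ranges are 48% to 78% (intended), 5% to 27% (reversed) and 69% to 83% (absolute).

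These figures show that the readings differ, not that anyone would choose a wrong one. In the example, item 11 would report a mean improvement of 0.4, well above the threshold, beside a reversed responder rate of 15%. For any symmetric distribution with a mean improvement above 0.22, more than half the subjects must be responders, so the mismatch would show in the same set of tables. An absolute reading would be harder to spot that way (76.9% against 61.8%), but it is also the least natural reading of a responder.

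**The case for a change.** The strongest argument for editing the text is that the definition does not stand on its own words. In this list, change from baseline is also applied to the SF-36, where higher is better, and to DAS28 and morning stiffness, where higher is worse, so the phrase carries no fixed sign. The protocol states direction in its other change-based response rules, and the correction is one phrase that leaves the threshold, data and other analyses alone. Since integrated analyses are planned under a separate SAP, more than one programmer may rely on the wording.

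All of that is true of the text. It does not show that a wrong result is likely. The argument has to set aside the word being defined and bring in a sign convention that the protocol does not contain. Nor is a protocol edit free: Section 17.1 requires a formal amendment for any modification. The sign of a derived variable is ordinary content for a SAP or a derivation specification, and Section 3.2.5 says the efficacy evaluations match those of the two primary studies, so the derivation is unlikely to be devised afresh from this one line.

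**Conclusion.** No change to the plan is needed. Item 12 lacks the word improvement, and that is a fair editorial remark. The endpoint's name, its place among efficacy endpoints and the protocol's usage elsewhere all point to a decrease in HAQ-DI of more than 0.22, and an analyst who follows the plan will compute that.

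The reach is small: one of 14 other secondary endpoints, summarised descriptively, with no hypothesis test. The primary endpoint (counts of subjects with specified safety events) and the major secondary endpoint (laboratory parameters) do not use the HAQ-DI, and item 11 reports the mean change in the same score.

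This conclusion rests on reading responders in its ordinary sense. It does not rest on the SAP, whose text could not be consulted here, or on the illustrative percentages, which come from assumed distributions. If the SAP or derivation specification already states a decrease, nothing remains open; if it does not, an analyst will write it that way as routine.

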11.3 Pharmacokinetic Analyses

Blood samples for the measurement of serum sirukumab concentrations and the detection of antibodies to sirukumab will be collected and analyzed.

Serum sirukumab concentration data including C_{trough} will be summarized by visit. PK data may be displayed graphically. If sufficient samples are collected, steady-state trough serum sirukumab concentrations before and after switching from PFS-U to PFS-AI will be evaluated.

11.4 Immunogenicity Analyses

The incidence of antibodies to sirukumab will be summarized for all subjects who have appropriate samples. Additional analysis may be performed as needed.

11.5 Pharmacodynamic Analyses

Changes in the concentration of individual pharmacodynamic markers from baseline to the selected post treatment time points will be summarized. Association between baseline levels and changes from baseline in select biomarkers and clinical response will be explored. Baseline value is defined as the baseline value of study CNT0136ARA3002 or CNT0136ARA3003, respectively. The pharmacodynamic analysis will characterize the response of subjects to sirukumab, to determine if loss of response to sirukumab can be predicted, and to better understand RA. Data will be summarized in a separate technical report.

11.6 Pharmacogenetics (DNA) Analyses

Pharmacogenetics tests will be summarized by treatment group. Genetic factors and changes in expression of DNA methylation markers from baseline (CNTO136ARA3002 and CNTO136ARA3003 studies) to the collection time point in study CNTO136ARA3004 will also be summarized. The pharmacogenetic analyses will be summarized in a separate technical report.

11.7 Health Economics Analyses

Change from baseline in total and domain scores of the WLQ and HECONQ will be summarized over time. Baseline value is defined as the baseline value of study CNTO136ARA3002 or CNTO136ARA3003, respectively.

11.8 Safety Analyses

Adverse Events

The verbatim terms used in the eCRF by investigators to identify AEs will be coded using the MedDRA dictionary. All reported AEs with onset during the treatment phase (ie, treatment-emergent AEs and AEs that have worsened since baseline) will be included in the analysis. For each AE, the percentage of subjects who experience at least 1 occurrence of the given event will be summarized by treatment group. Other safety analyses include the proportion of subjects with infections, SAE, AE leading to discontinuation.

Summaries, listings, datasets, or subject narratives may be provided, as appropriate, for those subjects who die, who discontinue treatment due to an AE, or who experience a severe or a serious adverse event (SAE).

Additional analyses will be performed for the number of subjects with cardiovascular SAEs by cardiovascular type and the number of subjects with malignancies by malignancy type (eg, lymphoma, nonmelanoma skin cancers, and other malignancies).

Clinical Laboratory Tests

Laboratory data will be summarized by type of laboratory test. NCI-CTCAE grades will be used in the summary of laboratory data. For some laboratory data, which are not covered in the NCI-CTCAE grading criteria, shift tables and/or other abnormal cutoff levels may be used for summaries. Descriptive statistics will be calculated for selected laboratory analyte at baseline and at each scheduled time point. A listing of subjects with post-baseline abnormal laboratory results based on NCI-CTCAE grades will also be provided.

Vital Signs

The proportion of subjects with markedly abnormal post-baseline values will be summarized.

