Sirukumab concentration (pharm serum sample) ^{c,d}				X
Antibodies to sirukumab (pharm serum sample) ^{c,d}				X
Ongoing Subject Review				
Injection-site evaluations	X			
Adverse events	X	X	X	X
Concomitant medications	X	X	X	X

a. Subjects who discontinue study agent injections and who are not terminating study participation should return for all scheduled follow-up assessments through approximately 16 weeks after the last study agent injection as specified in this table.
 
b. The first safety and efficacy follow-up visit should occur 4 weeks \pm 14 days after their last study agent injection. The visit window for follow-up assessments is \pm 14 days.
 
c. Pharm serum samples (sirukumab concentration and antibodies to sirukumab) will be collected at the final safety and efficacy follow up visit only from those subjects who had pharm serum samples collected at earlier time points in study CNTO136ARA3002 (approximately 750 subjects randomized in CNTO136ARA3002 before 18 November 2013) and from all subjects enrolled after participating in study CNTO136ARA3003.
 
d. Blood collected from one venipuncture will be divided into 3 serum aliquots (1 each for sirukumab concentration, antibodies to sirukumab and a backup sample). Refer to the Central Laboratory Manual for more detailed instructions.
				

ABBREVIATIONS

ACR	American College of Rheumatology
AE	adverse event
AI	Autoinjector
ALT	alanine aminotransferase
anti-HBc total	hepatitis B core antibody
anti-HBs	hepatitis B surface antibody
AST	aspartate aminotransferase
BD	Becton-Dickinson
BUN	blood urea nitrogen
CDAI	Clinical Disease Activity Index
CEC	Clinical Events Committee
CQ	chloroquine
CRF	case report form
CRP	C-reactive protein
CSR	Clinical Study Report
C _{trough}	Observed serum concentration immediately prior to the next administration
CV	cardiovascular
CYP	cytochrome P450
DAS28	Disease Activity Index Score 28
DBL	database lock
DMARD	disease modifying antirheumatic drugs
DMC	Data Monitoring Committee
DNA	deoxyribonucleic acid
DSUR	Development Safety Update Report
ECG	electrocardiogram
eCRF	electronic case report form
eDC	Electronic Data Capture
EULAR	The European League Against Rheumatism
Fc	fragment crystallizable
FDA	Food and Drug Administration
G	gauge
GCP	Good Clinical Practice
GH	Patient's Global Assessment of Disease Activity
GMS	Global Medical Safety
HAQ-DI	Health Assessment Questionnaire-Disability Index
HBsAg	hepatitis B surface antigen
HCQ	hydroxychloroquine

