3.2.3 Study Phases and Duration of Treatment

There will be 3 phases of this LTE study: Blinded active treatment, open-label treatment, and safety and efficacy follow-up.

CNTO 136 (sirukumab): Clinical Protocol CNTO136ARA3004 – Amendment 3

As described in Section 3.2.2, the blinded active treatment phase will continue until following 3 conditions have been met: the Week 52 DBL occurs in study CNTO136ARA3002, the Week 24 DBL occurs in study CNTO136ARA3003, and the last AI usability substudy subject completes the Week 16 visit or terminates from the study.

The open-label treatment phase of the study will begin after those 3 conditions have been met, and will continue through the last scheduled dose for all subjects. The safety and efficacy follow-up will include approximately 16 weeks of study evaluations following the last administration of study agent, including follow-up for patients who discontinued study treatment prior to their last scheduled dose. The safety and efficacy follow-up allows for monitoring of the subject for a period of equivalent to at least 5 times the half-life of sirukumab.

The maximum duration of the study is expected to be 156 weeks for subjects enrolling after participation in study CNTO136ARA3002 and 208 weeks for subjects enrolling after participation in study CNTO136ARA3003, followed by approximately 16 weeks of safety and efficacy follow-up after the administration of the final study agent injection of sirukumab.

After a minimum of 1 year treatment in CNTO136ARA3004 for subjects from study CNTO136ARA3002, or a minimum of 2 years of treatment in CNTO136ARA3004 for subjects from CNTO136ARA3003, and after sirukumab is approved for the treatment of RA in the subject's country of residence, the Sponsor may no longer offer study treatment in CNTO136ARA3004 for those specific subjects. At that point the subject will have the opportunity to discuss treatment options with their treating physician.

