9.1.4 Posttreatment Phase (Follow-Up)

At the end of the study, subjects will return for follow-up assessments through approximately 16 weeks after the last study agent administration. Subjects who discontinue study agent injections but do not terminate study participation will continue to have assessments performed for 16 weeks following last injection according to the Time and Events Schedule (Table 2).

Note: The visit that is approximately 16 weeks after the last study agent injection is referred to as the “final safety and efficacy follow-up visit” (Table 2).

In the event a subject discontinues study agent injections, the first safety and efficacy follow up visit should occur 4 weeks \pm 14 days after the date of the last administration of the study agent. The visit window for follow-up assessments is \pm 14 days.

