12.3 Procedures

12.3.1 All Adverse Events

All adverse events and special reporting situations, whether serious or non-serious, will be reported from the time a signed and dated ICF is obtained until completion of the subject's last study visit (which may include contact for follow-up of safety). SAEs, including those spontaneously reported to the investigator within 4 months after the last dose of study agent, must be reported using the Serious Adverse Event Form. The Sponsor will evaluate any safety information that is spontaneously reported by an investigator beyond the time frame specified in the protocol.

All events that meet the definition of a SAE will be reported as SAEs, regardless of whether they are protocol-specific assessments. Anticipated events will be recorded and reported as described in [Attachment 2](#). All adverse events, regardless of seriousness, severity, or presumed relationship to study therapy, must be recorded using medical terminology in the source document and the CRF. Whenever possible, diagnoses should be given when signs and symptoms are due to a common etiology (eg, cough, runny nose, sneezing, sore throat, and head congestion should be reported as "upper respiratory infection"). Investigators must record in the CRF their opinion

CNTO 136 (sirukumab): Clinical Protocol CNTO136ARA3004 – Amendment 3

concerning the relationship of the adverse event to study therapy. All measures required for adverse event management must be recorded in the source document and reported according to Sponsor instructions.

The Sponsor assumes responsibility for appropriate reporting of adverse events to the regulatory authorities. The Sponsor will also report to the investigator all SAEs that are unlisted (unexpected) and associated with the use of the drug. The investigator (or Sponsor where required) must report these events to the appropriate IEC/IRB that approved the protocol unless otherwise required and documented by the IEC/IRB.

Subjects (or their designees, if appropriate) must be provided with a "study card" indicating the following:

- Subject number
- Study site number
- Study number
- Sponsor's emergency contact name and 24-hour telephone number (for medical staff only)
- Investigator's name and contact information
- Statement in the local language(s) that the subject is participating in a clinical trial.

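### Section 11.8 ties the general AE summary to onset in the treatment phase, so AEs that start in the separate 16-week follow-up are collected but, read literally, not summarised

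*Protocol*

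**What the plan says.** Protocol Section 11.8, under Adverse Events, states which events enter the analysis: "All reported AEs with onset during the treatment phase (ie, treatment-emergent AEs and AEs that have worsened since baseline) will be included". It then gives, for each AE, the percentage of subjects affected by treatment group, and adds: "Other safety analyses include the proportion of subjects with infections, SAE, AE leading to discontinuation". That added sentence has no onset window. Summaries, listings and narratives for deaths, serious events and discontinuations due to AEs are optional.

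Section 3.2.3 sets out the phases: "There will be 3 phases of this LTE study: Blinded active treatment, open-label treatment, and safety and efficacy follow-up". It says that the open-label phase "will continue through the last scheduled dose for all subjects". It places about 16 weeks of evaluations after the last administration in the third phase, including for subjects who stop early, and justifies that length because it "allows for monitoring of the subject for a period of equivalent to at least 5 times the half-life of sirukumab". The title of Section 9.1.4 labels the same period "Posttreatment Phase (Follow-Up").

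AE collection continues through follow-up. Table 2 reviews AEs at Weeks 4, 8, 12 and 16 after the last injection, and its footnote a says: "Subjects who discontinue study agent injections and who are not terminating study participation should return for all scheduled follow-up assessments". Section 12.3.1 has AEs reported from consent to the last study visit.

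Elsewhere in Section 11 the window is longer. The primary safety events (11.2.1), laboratory toxicity grades (11.2.2) and other secondary endpoints (11.2.3) are all summarised to the end of the study.

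**The concern.** Long-term safety is the primary objective, and the follow-up phase exists to observe subjects while drug is cleared. An inclusion rule tied to the treatment phase omits from the main AE table exactly the events that this phase was added to capture. Sections 11.2.1 to 11.2.3 state an end-of-study window explicitly; the AE rule in 11.8 does not, so a programmer who follows the text would reasonably stop at the end of treatment, while another might apply a customary post-dose window. The two would produce different tables.

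The practical stake is non-primary events. Section 9.8 names infections in general as events of interest, but only serious infections are in the primary count. If the onset rule also governs the infection proportion, a non-serious infection that starts in follow-up has no assured summary. The same would hold for a serious AE outside the four primary types.

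**Working it through.** There is no stated figure to reproduce. The check is a comparison of passages, followed by one calculation of scale.

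**Passages side by side**

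| Output | Section | Window stated | Follow-up onset included? |
|---|---|---|---|
| General AE summary | 11.8 | Onset in the treatment phase | No, read literally |
| Proportions with infections, SAEs | 11.8, same paragraph | None | Unclear; possibly not |
| Cardiovascular SAEs, malignancies, serious infections, GI perforations | 11.2.1 | End of study | Yes |
| Adjudicated serious cardiovascular events | 11.2.1 | None of its own; sits under the primary endpoint | Not cut off by the 11.8 rule |
| Toxicity grades (neutrophils, platelets, hepatobiliary, lipids) | 11.2.2 | End of study | Yes |
| General safety summary in the Synopsis | Synopsis, Safety Analyses | None | Not stated |

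The step to exclusion is this: 11.8 says which AEs enter the analysis and makes treatment-phase onset the condition; 3.2.3 and 9.1.4 place follow-up outside the treatment phases; the Protocol has no definition of treatment-emergent that reaches past the last dose.

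**Scale: follow-up as a share of scheduled observation time**

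Inputs: follow-up f = 16 weeks (3.2.3); maximum treatment t = 156 weeks for subjects from CNTO136ARA3002 and 208 weeks for those from CNTO136ARA3003 (3.2.3); follow-up visit window of plus or minus 14 days (Table 2, footnote b), so f ranges from 14 to 18 weeks.

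Formula: share = f / (t + f).

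- t = 208: 16/224 = 7.1% (14/222 = 6.3% to 18/226 = 8.0%)
- t = 156: 16/172 = 9.3% (14/170 = 8.2% to 18/174 = 10.3%)

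The share rises only when treatment is shorter. If supply stopped on local approval at the earliest time allowed by Section 10.2, item 16:

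- t = 104 (from CNTO136ARA3003): 16/120 = 13.3%
- t = 52 (from CNTO136ARA3002): 16/68 = 23.5%

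These are shares of time. The documents give no AE rates, so they cannot be turned into a number of omitted events.

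**The case against.** The strongest reply is that treatment-emergent is a term of art that often carries a post-dose window, and that such a window normally sits in the SAP. The SAP text was not available for this review, so a definition there can be neither confirmed nor called missing. This stands, and it limits the point to the wording of the Protocol. It does not remove it, because 11.8 equates the term with onset in the treatment phase.

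It is also true that 11.8 does not say *only* and does not expressly exclude follow-up onset, and that the Synopsis states no window. The sponsor may intend full coverage. Still, a sentence that says which events enter an analysis defines the set.

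The boundary is unclear for early discontinuers. Section 3.2.3 ends open-label treatment at the last scheduled dose; read study-wide, their follow-up could overlap the treatment phase, although the same section places it in the follow-up phase.

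A reader might infer three stronger things that the documents do not support:

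- **That follow-up SAEs and infections are definitely excluded.** Their sentence has no window; extending the onset rule to them is an inference from their position in the paragraph. AEs leading to discontinuation should be little affected, since study agent has already stopped by follow-up.
- **That a follow-up death could go unexamined.** Sections 3.1, 3.2.6 and 11.11 put death on the Clinical Events Committee's list without a cardiovascular qualifier. What remains is that a death judged non-cardiovascular may not appear in the adjudicated cardiovascular summary.
- **That 13% to 24% of observation is lost.** Those shares need local approval and a stop at the earliest permitted time.

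**Conclusion.** The point holds as a minor one. As written, 11.8 leaves AEs with onset in follow-up out of the general AE summary, although they are collected and the Protocol gives a safety reason for collecting them. The affected period is about 7% to 9% of scheduled observation time at the planned maximum durations, and more only for early discontinuers or a stop on local approval.

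The study is descriptive, with no hypothesis test, and its primary safety counts run to the end of the study, so no primary conclusion depends on this. The verdict rests on two assumptions: that the treatment phase in 11.8 means the blinded and open-label phases of 3.2.3, and that no post-dose window is defined elsewhere. If the SAP defines treatment-emergent through the final follow-up visit, only a wording mismatch is left.

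**What to change.** Amend 11.8 so that the AE, SAE and infection summaries include events with onset from the start of this study through the final safety and efficacy follow-up visit, and show them split into on-treatment and follow-up onset. State how the split is made for subjects who stop early. If the SAP already defines treatment-emergent through that visit, align the 11.8 wording to it instead.

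The cost is a sentence or two and one extra tabulation; AEs are already collected at all four Table 2 visits. The downside is that some follow-up events may reflect later RA therapy, because Section 6.4 bars the prohibited drugs only while study agent is being received. The split by onset makes this visible.
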